5.1 Inclusion criteria

- Age ≥ 18 years
- Clinical diagnosis of epithelial ovarian, peritoneal or fallopian tube cancers
- Recurrent or progressive disease (CA125, radiological or clinical)
- ECOG PS 0-3
- Life expectancy > 3 months
- Planning to start chemotherapy within 2 weeks of registration
- Able to complete questionnaires independently.

6.0 STUDY METHODS

6.1 Registration

Patients will commence treatment within 2 weeks of registration. Patients can be registered by faxing an enrolment form to the NHMRC Clinical Trials Centre at [name]

6.2 Treatment

This is not a treatment study. The type, duration and frequency of chemotherapy, biological therapy (targeted therapies) will be at the discretion of the treating physician. All supportive therapies and concomitant medications will be given as per usual local practice.

[figure not shown]
6.3 Duration of the study

Stage 1

Data will be collected at baseline, prior to every treatment cycle for 4 treatment cycles (12 – 16 weeks) and one month post completion of treatment or until disease progression, *whichever comes first*

Stage 2

Data will be collected at baseline, prior to every treatment cycle, 3-4 weeks following completion of chemotherapy, and then 3-4 weekly until disease progression; *whichever comes last*.

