6.4 Study Schema**7.0 OUTCOME ASSESSMENTS****7.1 Patient Reported Outcomes**

Patients in stages 1 and 2 will fill out the following questionnaires at the intervals outlined below. It is estimated that it will take 20 - 30 minutes to complete these questionnaires. The measures selected cover the domains of perceived severity of symptoms, quality of life and hope. The measures are psychometrically sound and have been previously found to be sensitive to change and acceptable to ovarian cancer populations.

Stage 1

QoL Instrument	Baseline (within 2 weeks before first cycle)	Before every subsequent cycle of treatment q3 – 4 weekly	4 weeks after starting 4th cycle of treatment or after end of treatment
SRQ	X	X	X
FACT-O	X	X	X
QLQ-C30 + Ov-28	X	X	X
Pt DATA Form	X	X	X
Expected & perceived benefit	X	X	X
HADS	X		X
Herth Hope Index	X		X

Stage 2

QoL Instrument	Baseline (within 2 weeks before first cycle)	Before every subsequent cycle of treatment or until disease progression – whichever comes last* q 3 – 4 weekly	Before cycle 3 (3-4 weeks after day 1 of cycle 2)
MOST (recent status)	X	X	X
MOST (change)			X
FACT-O	X	X	X
EORTC QLQ C30 + Ov-28	X	X	X
Expected Benefit Scale	X	X	X
Perceived Benefit Scale		X	X

*includes those patients who cease study treatment but do not progress and continue with follow-up

MOST (change)

This data will only be collected at Cycle 3 and used to determine the minimal clinically important difference which is the primary aim of the study.

Questionnaires to be completed at each time point:**Baseline:**

1. MOST – Recent

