methodology has been used previously to determine the minimum clinically important difference in similar contexts (30, 31). The general approach for assessing improvements will be to calculate absolute changes from baseline. Various criterion levels (e.g. 1, 1.5 and 2 points on a 10 point scale) and durations (e.g. 3 and 6 weeks) or improvement will be assessed to determine a criterion that is both sensitive (avoids false negatives – missing true benefit) and robust (avoids false positives). Relative changes from baseline will also be examined (e.g. 50% reduction from the baseline score). This approach will be applied primarily to individual symptoms, but also to domain subscales (e.g. physical wellbeing, emotional wellbeing) and total scores (e.g. FACT-G overall wellbeing). It is anticipated that benefits will be much more evident in individual symptoms than in domain subscales or total scores.

Since the MOST has been constructed as a comprehensive measure of all the relevant symptoms for this patient population, a *global symptom benefit* measure will also be examined which combines the first 17 items of MOST and constructs a weighted average of these and item 18 (details of this methodology are provided in Lumley et al (Statistics in Medicine 2000)).

Secondary objectives:

To evaluate the proportion of women benefiting from palliative chemotherapy as defined by a clinically significant improvement in HRQL scores, the relationship between changes in perceived symptoms, HRQL, anxiety and depression and objective tumour response.

Each patient's subjective responses will be categorized as having improved, worsened or remained stable in comparison to baseline according to the criteria defined above.

Best objective tumor response will be categorized as complete or partial response, stable disease, or progressive disease using RECIST and GCIG definitions of response. 3x3 tables of subjective response versus tumour response will be presented.

Subjective response will be further categorised dichotomously as improved or not by combining the stable and worsened groups. To assess the relationship between improvement in subjective responses and improvements in tumour response, 3x2 tables of subjective response versus tumour response will be analysed using a test for trend.

Time to event endpoints will be analysed using the Kaplan-Meier method.

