Appendix 1 Patient Assessment Schedule

Tests & Observations	Registration Baseline	Pre-each cycle of treatment until progression	Pre-cycle 3 ¹	Every 6-8 weeks until progression/off study	3 – 4 weeks post last cycle of study treatment	3 monthly following progression ²
Informed Consent	X					
History	X					
Physical Exam	X	X				
Performance Status (ECOG)	X					X
FIGO stage at initial diagnosis	X					
Life expectancy > 3 months	X					
Type of resistance: (see NOTES) 1. Primary Platinum Resistant 2. Primary Platinum Refractory 3. Secondary Platinum Resistant 4. Secondary Platinum Refractory	X					
Height and weight	X					
Estimated weight 3/12 ago	X					
Date cancer 1 st diagnosed	X					
Debulking at initial diagnosis? If yes, status ³	X					
Secondary debulking surgery for recurrence?	X					
No. of lines of previous treatment for OC	X					
Response to most recent line of therapy ⁴	X					
Date of completion of last line of therapy	X					
Date chemotherapy planned to commence	X					
Regimen – drug name, dose, frequency	X					
Reasons for proposed treatment ⁵	X					
Investigator Questions: Predicted likelihood of objective response, symptom improvement, how many cycles of treatment do you expect to administer, life expectancy in months (this information must be obtained from the investigator)	X					
Symptoms						
Cancer related symptoms	X					
Symptomatic ascites	X					
Symptoms of cramping abdominal pain or intermittent/incomplete bowel obstruction?	X					

Tests & Observations	Registration Baseline	Pre-each cycle of treatment	Pre-cycle 3	Every 6-8 weeks until progression/off study	3 – 4 weeks post last cycle of study treatment	3 monthly following progression ²
Tumour Related						
Pathology ⁶	X					
Grade at initial diagnosis ⁷	X					
Extent of disease ⁸	X					
Sites of disease ⁹	X					
Pre-Treatment Blood Tests **please note** these may not all be routine for your site						
Absolute Neutrophil Count (ANC)	X					
Platelets	X					
Lymphocytes	X					
Haemoglobin	X					
Serum Albumin	X					
Alkaline Phosphatase	X					
C Reactive Protein	X					
LDH (lactate dehydrogenase)	X					
CA-125	X			X ¹⁰		
CA-125 Velocity¹¹	X					
Toxicities						
Toxicity Data ¹²	X					
Adverse Events ¹³		X				
Tumour Response						
Tumour Response Assessment ¹⁴				X		
Response ¹⁵				X		
Method of Assessment ¹⁶				X		
Response ¹⁷				X		
Symptom benefit or deterioration ¹⁸				X		
Follow-up						
Patient status ¹⁹						X
Has the patient progressed? ²⁰						X

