Reason for ceasing treatment ²¹						X
Current treatment ²²						X
Death notification ²³						
Please complete at notification of patient death						
QoL Questionnaires						
Baseline Booklet ²⁴	X					
Each cycle of treatment booklet ²⁵		X				
Cycle 3 additional questions booklet ²⁶			X			
Post last cycle of study treatment booklet ²⁷					X	

NOTES:

- ¹ Additional questions at Cycle 3. To be completed by the patient in addition to the "Each cycle of treatment" booklet
- ² **OR:** every three weeks until progression for those who have ceased study treatment but not progressed, and then three monthly after progression
- ³ Status = No residual disease, Residual disease <1cm, Residual disease >1cm, Not applicable, Unknown
- ⁴ Response = CR (complete response), PR (partial response), SD (stable disease), PD (progressive disease), NE (not evaluable)
- ⁵ Reasons = Symptom control/palliation, if asymptomatic, to delay the development of symptoms, Rising CA125, Radiological evidence of progression
- ⁶ Serous, endometrioid, clear cell, mucinous, transitional, undifferentiated, mixed – please specify, other – please specify
- ⁷ Low Grade or Hi Grade (includes 2 and 3)
- ⁸ Elevated CA125 or measurable disease. If measurable disease, please indicate maximum diameter of largest tumour
- ⁹ Intra-peritoneal tumour, Nodal, Liver/spleen, Lung, Other
- ¹⁰ CA125 at 6 – 8 weekly only if using CA125 as the Method of Assessment – actual value is not required
- ¹¹ Include 3 most recent CA-125 levels in the three months prior to commencing chemotherapy with dates
- ¹² Symptoms/pre-existing toxicities present at study enrolment
- ¹³ Adverse Events from treatment
- ¹⁴ Complete the Tumour Response Assessment at 6 – 8 weekly intervals ie. after every second cycle of chemotherapy using CA125, clinical or radiological assessment criteria
- ¹⁵ Has there been a response since the last assessment?
- ¹⁶ What was the method of assessment? CA125, clinical assessment, radiological assessment (RECIST). The method of assessment is at the physician's discretion
- ¹⁷ What was the response? CA125, Clinical response, Radiological response (according to RECIST criteria)
- ¹⁸ Has there been any symptom benefit or symptom deterioration?
- ¹⁹ Is the patient alive or dead?
- ²⁰ If the patient is alive, has she progressed?
- ²¹ Please list the reason for ceasing treatment ie. completed planned no. of cycles, AE, Tumour progression, clinician preference, patient preference, death, other

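### Appendix 1 schedules no questionnaire between the post-treatment form and progression, although sections 6.3 and 7.1 require one every 3-4 weeks

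*Protocol*

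**What the plan says.** **Body of the protocol.** Section 6.3 sets Stage 2 collection at baseline, before every cycle, and then "3-4 weeks following completion of chemotherapy, and then 3-4 weekly until disease progression". The Stage 2 table in section 7.1 heads its repeat-questionnaire column "Before every subsequent cycle of treatment or until disease progression – whichever comes last* q 3 – 4 weekly". Its asterisked footnote says that the column "includes those patients who cease study treatment but do not progress and continue with follow-up".

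**Appendix 1.** Four questionnaire rows appear, each with a single mark: the baseline booklet at registration, the each-cycle booklet before each cycle, the additional questions before cycle 3, and the row "Post last cycle of study treatment booklet" at 3-4 weeks after the last cycle. The final column is for follow-up. Note 2 extends it to visits "every three weeks until progression for those who have ceased study treatment but not progressed, and then three monthly after progression". That column is marked for ECOG status, patient status, progression, reason for ceasing treatment and current treatment. It has no questionnaire mark.

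**Other text on the form.** Note 25 defines the each-cycle booklet by cycle, starting before cycle 2. The description of the MOST in section 7.1, repeated in Appendix 3, likewise gives the recent status form before each cycle of chemotherapy and mentions no off-treatment use.

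**Endpoints that depend on these forms.** Section 8.0 lists time to symptom deterioration and duration of symptom improvement as Stage 2 secondary endpoints. Section 3.0 lists the matching objectives.

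**The concern.** The two parts of the protocol give different instructions for the same women: those who have stopped chemotherapy and have not progressed. The body wants a questionnaire every 3-4 weeks. The schedule brings these women back every three weeks and gives them none.

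These are the women in whom lasting benefit would show. If a woman's symptoms improved on treatment and stayed improved, the end of that improvement lies after the last form that Appendix 1 asks for. A missing form cannot be rebuilt at analysis, so a statistical analysis plan cannot repair the loss.

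**Working it through.** **1. The passages side by side (Stage 2, off treatment, not progressed)**

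| Source | Visit | Questionnaire |
|---|---|---|
| 6.3 | every 3-4 weeks to progression | data collection required |
| 7.1 table and footnote | every 3-4 weeks to progression | required |
| Appendix 1, post-last-cycle column | once, 3-4 weeks after last cycle | marked |
| Appendix 1, follow-up column with Note 2 | every three weeks to progression | not marked |
| Appendix 1, Note 25 | before each cycle | tied to cycles |
| MOST description (7.1, Appendix 3) | before each cycle | tied to cycles |

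The reading does not hang on how the table's columns line up. Each booklet row has only one mark, and no row is named for off-treatment follow-up.

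**2. The plan's own figures.** The protocol states no number for the two symptom-duration endpoints, so there is none to reproduce. The sample-size interval does reproduce: 1.96 × √(0.5 × 0.5 / 600) = 0.040, giving 46% to 54%. It rests on evaluable data after 2 cycles, so the schedule conflict does not touch it.

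**3. How many women could be affected (illustration)**

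Inputs:
- Median time to progression M of 9.1 and 13.6 weeks, which section 1.0 quotes for platinum-resistant patients in a comparison of two drugs.
- Assumed: 4 or 6 cycles (k) of 3 or 4 weeks (w), exponential progression times, and every unprogressed woman stopping after k cycles.

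The last Appendix 1 form falls at c = k × w + w weeks, counting the 3-4 weeks from the end of the last cycle. The share still progression-free is S(c) = exp(−ln 2 × c / M).

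| Cycles × weeks | c (weeks) | S(c), M = 9.1 | S(c), M = 13.6 |
|---|---|---|---|
| 4 × 3 | 15 | 32% | 47% |
| 4 × 4 | 20 | 22% | 36% |
| 6 × 3 | 21 | 20% | 34% |
| 6 × 4 | 28 | 12% | 24% |

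The range is 12% to 47%, or about 71 to 279 women per 600.

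If the 3-4 weeks are counted from day 1 of the last cycle instead, c = k × w, which is 12 to 24 weeks. The range becomes exp(−ln 2 × 24 / 9.1) = 16% to exp(−ln 2 × 12 / 13.6) = 54%.

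**4. How much follow-up each would lose.** Under the same exponential assumption, the median further time to progression from the last form is again 9.1 to 13.6 weeks. At three-weekly visits, half of these women would miss at least 3 (9.1 / 3 = 3.0) to 4 (13.6 / 3 = 4.5) forms.

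**The case against.** **The header of the each-cycle column.** On the first page of Appendix 1 it reads "Pre-each cycle of treatment until progression", which can be taken as carrying the booklet on to progression. This has some force but does not settle the matter. A woman off treatment has no next cycle, Note 25 ties the booklet to cycles, and the header repeated above the continued table drops the reference to progression. Read literally, it would also end forms at progression while cycles continue, against the later-of-two rule in section 7.1.

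**The body text does require the forms.** This is correct. The loss is conditional: it occurs at sites that work from Appendix 1, and the protocol does not say which part governs. It would be too strong to say that the endpoints cannot be observed.

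**Appendix 1 has another record of symptoms.** A row on symptom benefit or deterioration is marked every 6-8 weeks until progression or off study. It sits with the tumour response items and is not a patient questionnaire. It cannot supply the scores on which the study's criteria for benefit are to be built.

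**A stronger reading that the documents do not support.** Section 9.2 states "Time to event endpoints will be analysed using the Kaplan-Meier method", and a reader might infer that the symptom endpoints will be biased by informative censoring. That does not follow.
- An earlier last form shortens follow-up. It biases Kaplan-Meier only if the time of stopping treatment depends on symptom course.
- In a simulation with an assumed median of 20 weeks to deterioration, a median of 16 weeks to stopping treatment (capped at 24 weeks) and a last form 4 weeks later, the true 20-week deterioration-free share was 50%. Kaplan-Meier gave 49.9% with independent stopping, 53.3% and 56.2% at correlations of 0.3 and 0.6, and 45.9% at −0.3. The direction is not fixed, and the documents do not establish any dependence.
- The protocol gives no event definition or censoring rule for these endpoints and defers detail to a statistical analysis plan that is not at hand.
- Treating progression as a competing event is a choice of estimand, since symptoms can still worsen after progression.

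**Conclusion.** The contradiction is real and can be confirmed by reading the protocol alone. Sections 6.3 and 7.1 require off-treatment questionnaires up to progression. Appendix 1 omits them, and Note 25 and the MOST text lean the same way as the appendix.

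The consequence is loss of patient-reported follow-up for two secondary endpoints where Appendix 1 is followed. About 12% to 47% of women would still be progression-free at their last form (16% to 54% on the shorter count). These shares are illustrative: they assume exponential progression at medians taken from another study's platinum-resistant subset, and a fixed 4 to 6 cycles. Longer treatment would lower them, and early stopping without progression would raise them.

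The work on the minimum important difference is untouched, because its change form is given before cycle 3. How progression and death enter the symptom time-to-event analyses is a matter for the statistical analysis plan and forms no part of this point.

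**What to change.** 1. In Appendix 1, mark the each-cycle booklet in the follow-up column for the three-weekly visits before progression described in Note 2.
2. Reword the each-cycle column header (on both pages), Note 25 and the MOST description in section 7.1 and Appendix 3, so that they match section 6.3 and the later-of-two rule in the 7.1 table.
3. In the same edit, reconcile the visit interval, which is 3-4 weekly in sections 6.3 and 7.1 but three-weekly in Note 2.

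The cost is a correction to one table and a few lines of text. No new instrument or visit is needed, since Note 27 already reuses the each-cycle booklet after treatment. Women at sites that had followed Appendix 1 would complete some extra forms, at an estimated 20-30 minutes per set in section 7.1, but section 6.3 already asks this of them.

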6.4 Study Schema**7.0 OUTCOME ASSESSMENTS****7.1 Patient Reported Outcomes**

Patients in stages 1 and 2 will fill out the following questionnaires at the intervals outlined below. It is estimated that it will take 20 - 30 minutes to complete these questionnaires. The measures selected cover the domains of perceived severity of symptoms, quality of life and hope. The measures are psychometrically sound and have been previously found to be sensitive to change and acceptable to ovarian cancer populations.

Stage 1

QoL Instrument	Baseline (within 2 weeks before first cycle)	Before every subsequent cycle of treatment q3 – 4 weekly	4 weeks after starting 4th cycle of treatment or after end of treatment
SRQ	X	X	X
FACT-O	X	X	X
QLQ-C30 + Ov-28	X	X	X
Pt DATA Form	X	X	X
Expected & perceived benefit	X	X	X
HADS	X		X
Herth Hope Index	X		X

Stage 2

QoL Instrument	Baseline (within 2 weeks before first cycle)	Before every subsequent cycle of treatment or until disease progression – whichever comes last* q 3 – 4 weekly	Before cycle 3 (3-4 weeks after day 1 of cycle 2)
MOST (recent status)	X	X	X
MOST (change)			X
FACT-O	X	X	X
EORTC QLQ C30 + Ov-28	X	X	X
Expected Benefit Scale	X	X	X
Perceived Benefit Scale		X	X

*includes those patients who cease study treatment but do not progress and continue with follow-up

MOST (change)

This data will only be collected at Cycle 3 and used to determine the minimal clinically important difference which is the primary aim of the study.

Questionnaires to be completed at each time point:**Baseline:**

1. MOST – Recent
2. EORTC QLQC30/OV28
3. FACT-O
4. Expected Benefit Scale

Each Cycle or until progression

1. MOST – Recent
2. EORTC QLQC30/OV28
3. FACT-O
4. Expected & Perceived Benefit Scale

Additional Questions for Cycle 3 only – in addition to ‘Each Cycle or until progression’ booklet

1. MOST – Change

3 – 4 weeks post last cycle of study treatment

1. MOST – Recent
2. EORTC QLQC30/OV28
3. FACT-O
4. Expected & Perceived Benefit Scale

Stage 1

Symptom Representation Questionnaire (SRQ) (26)

A wide variety of cancer symptom assessment instruments exist but there are limitations to the existing instruments particularly with respect to the study we have in mind. A group in Pittsburgh have recently developed and validated an instrument called the Symptom Representation Questionnaire (SRQ) (12). The SRQ is designed to provide a multi-dimensional assessment of multiple cancer-related symptoms. It was derived from information processing theory and assesses critical cognitive and emotional factors that are known to influence coping and outcomes. It has been validated in women with ovarian cancer. The SRQ is designed to assess the severity of 26 cancer-related symptoms followed by an assessment of five additional important dimensions of a person's three most bothersome symptoms. It appears to be a psychometrically sound and versatile instrument for assessing cognitive and emotional representations of a wide variety of cancer-related symptoms.

Functional Assessment of Cancer Therapy – Ovary (FACT-O) (27)

The (Functional Assessment of Cancer Therapy) FACT-G is a self reported measure that assesses four dimensions of well-being: physical, functional, social/family and emotional well-being. An ovarian cancer-specific subscale of the FACT has been developed and can be combined with the FACT-G subscales. Together, these scales are referred to as the FACT-O which consists of 38 items. It has been previously validated and found appropriate as a brief QoL assessment in clinical trials and descriptive studies.

EORTC QLQ-C30 + QLQ-Ov28 (28)

The QOL Core Questionnaire 30 (QLQ-C30) was designed by the European Organization for Research and Treatment of Cancer (EORTC) Quality of Life Group in 1991. It initially comprised of 36 items, but has undergone multiple revisions with improvements in the scales which has resulted in the present 30 item measure (EORTC QLQ-C30 version 3), now the most widely used measure in oncology. The ovarian cancer module addresses additional important symptoms and concerns not included in QLQ-C30, and like all EORTC modules, is designed to be used in conjunction with the QLQ-C30.

Patient DATA Form (29)

This is a validated 47 item instrument rating a range of symptoms, concerns and functions important to people with advanced cancer. The troublesomeness of each symptom is rated on a uniform scale from 0 = "none at all" to 10 = "worst I can imagine"

Expected and Perceived Benefit

At baseline and before starting chemotherapy patients will answer 'How much do you expect your symptoms to improve with chemotherapy?' using a numeric rating scale from 0 = "none at all" to 10 = "completely". At each of their follow up visits, after starting chemotherapy and **prior** to objective assessment of response, patients will answer: "How much have your symptoms improved with chemotherapy?" using the same scale. Finally, if patients indicate an improvement in symptom control, they will be asked to complete one item on a 5 point Likert scale (ranging from not at all to very much so) asking whether their symptom improvement was enough to affect their overall quality of life.

HADS (30)

The Hospital and Anxiety Depression Scale is comprised of 14 items in 2 subscales independently measuring anxiety and depression.

Herth Hope Index (31)

The Herth Hope Index measures the degree to which a patient feels they feel help and a sense of meaning in their lives. The scale has three subscales: temporality and future, positive readiness and expectancy, and interconnectedness.

Stage 2

The rationale for the measures included in Stage 2 is presented in Appendix 1, which provides a brief report of Stage 1 analyses. In summary, there was little to differentiate the candidate instruments in terms of distributions of baseline or change scores, so the choice of instruments for inclusion in Stage 2 was largely determined by coverage of the symptoms and aspects of QOL as those most noticed by Stage 1 patients.

MOST – Measure of Ovarian Cancer Symptoms and Treatment Concerns

The MOST is an ovarian cancer symptom benefit instrument, devised specifically for this study. It comprises 35 individual items which provide comprehensive coverage of all the symptoms and aspects of QOL identified as those most noticed by Stage 1 patients in this study and corroborated in a cohort of 421 women dying of ovarian cancer. (32). Each item is on a discrete scale of 0-10, where major symptomatic distress is represented by 10. It is an adaptation of the Pt-DATA form based on the results of the Stage 1 analysis. The changes include additions (two additional items: abdominal bloating and abdominal pain) and deletions (items which were deemed irrelevant to this clinical context, and clinical opinion of the investigators).

There are two forms:

1. Recent status
2. Change in status

The recent status form asks patients to report their perceived levels of symptoms and concerns 'on average during the last 3-4 weeks'. It is divided into sections. The first section addresses disease related symptoms and concerns (18 items). The first 15 of these items refer to disease symptoms and have an objective interpretation by patients. Items 16 and 17 refer to physical and emotional well-being whilst item 18 is a question referring to overall well-being. The second section addresses additional treatment related concerns (17 items). This is an adaptation of the Pt-DATA form based on the results of the Stage 1 analysis. The changes include additions (two additional items: abdominal bloating and abdominal pain) and deletions (items which were deemed irrelevant to this clinical context, and clinical opinion of the investigators).

The change form includes the same items as the recent status form, but asks patients to report their perceived change in levels of symptoms and concerns since 'before you started this course of chemotherapy 6-8 weeks ago'. The recent status form will be administered prior to each cycle of chemotherapy, while the change form will be administered only prior to the third cycle of chemotherapy. The change form will be used to help determine the minimum clinically important difference in the status form scores, as has been done previously (33, 34)

Functional Assessment of Cancer Therapy – Ovary (FACT-O) EORTC QLQ-C30 + QLQ-Ov28

The decision to include both QLQ-C30/OV28 and FACT-O was based on the need to be able to conduct a robust validation of the MOST against the two current leading candidates for measuring ovarian-specific HRQOL.

Expected and Perceived Benefit

At baseline and before starting chemotherapy patients will be asked to answer 'How much do you expect your symptoms to improve with chemotherapy?' using a numeric rating scale from 0 = "none at all" to 10 = "completely". After their 2nd cycle, and after their final cycle of chemotherapy, patients will be asked: "How much have your symptoms improved with chemotherapy?" using the same scale. If patients indicate an improvement in symptom control, they will be asked to answer the question "How much better is your overall quality of life as a result of your symptoms improving?" on a 4-point, ordinal scale (No better, a little better, moderately better, much better). Patients will also be asked to answer "On balance, how worthwhile has this course of chemotherapy been for you" on a 4-point, ordinal scale (not at all, somewhat, moderately, extremely).

